HbA1c	X		X			X		X		X	X	X
Fasting glucose	X		X			X		X		X	X	X
Total and active GLP-1/GIP			X			X		X		X	X	
7-point SMBG			X ¹							X ^j		
PK ^k						X		X		X	X	X
Immunogenicity			X			X		X		X	X ¹	X
Nonpharmacogenetic stored samples			X							X		

Abbreviations: AE = adverse event; BG = blood glucose; BP = blood pressure; ECG = electrocardiogram; eGFR = estimated glomerular filtration rate; ET = Early Termination; FSH = follicle-stimulating hormone; GLP-1 = glucagon-like peptide-1; GIP = glucose-dependent insulinotropic peptide; HbA1c = hemoglobin A1c; IWRS = interactive web response system; LH = luteinizing hormone; PK = pharmacokinetics; PR = pulse rate; SMBG = self-monitoring of blood glucose; T = telephone visit; TE = treatment emergent; Term. = termination.

- a Telephone visits occur during the week following a dose escalation and should be done 3 to 6 days after a site visit for dose escalation and administration. At telephone visits, the sites should call the patient, ask how the patient is, and ask whether the patient would like to come to the site for assistance with the next study drug dilution and administration. Sites should also remind patients to write down any AEs in their diaries at the telephone visits (as well as at all site visits).
- b Visit should occur approximately 1 week after the last dose (Dose 12).
- c Additional physical examinations may be performed throughout the study if determined necessary due to patient symptoms.
- d Visit should occur 4 weeks after the last dose of study drug or 3 weeks after Visit 10.
- e ECGs should be collected prior to all blood draws and study drug administrations. Local ECGs will be collected for screening (Visit 1) and Early Termination. Centralized ECGs, collected in supine position and in triplicate, should be collected for all other designated visits.
- f Screening laboratory tests include serum hepatitis B surface Ag, hepatitis C antibody (Ab), and human immunodeficiency virus (HIV) Ab tests for all patients (see Appendix 2).
- g Serum pregnancy test will be performed by central laboratory at Visit 1 for women of child-bearing potential. For the remainder of the study, a urine pregnancy test may be performed at the investigator's discretion if pregnancy is suspected during the study (local laboratory). A urine pregnancy test (local) should be given to all women of child-bearing potential at Visit 3 prior to administration of first dose of study drug to confirm lack of pregnancy.

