6.2. Exclusion Criteria

Patients will be excluded from study enrollment if they meet any of the following criteria at screening:

Medical Conditions

- [9] Have type 1 diabetes mellitus or latent autoimmune diabetes in adults.
- [10] Have uncontrolled diabetes defined as an episode of ketoacidosis or hyperosmolar state requiring hospitalization.
- [11] Have had an episode of severe hypoglycemia, as defined by the occurrence of neuroglycopenic symptoms requiring the assistance of another person for recovery, within 6 months prior to Visit 1, or have a history of hypoglycemia unawareness or poor recognition of hypoglycemic symptoms. Any patient that the investigator feels will not be able to communicate an understanding of hypoglycemic symptoms and the appropriate treatment of hypoglycemia should also be excluded.
- [12] Have a history of acute or chronic pancreatitis or elevation in serum lipase/amylase (greater than 2 times the upper limit of normal [$>2 \times \text{ULN}$]) or fasting serum triglyceride level of >500 mg/dL at screening.
- [13] Have a diagnosis of gastroparesis or history of bariatric surgery or a clinically significant gastric emptying abnormality, in the opinion of the investigator.
- [14] Have active proliferative diabetic retinopathy.
- [15] Have known liver disease, obvious clinical signs or symptoms of liver disease, acute or chronic hepatitis, or alanine aminotransferase (ALT) levels $>2.5 \times \text{ULN}$ at Visit 1, as determined by the central laboratory at screening.
- [16] Have a known self or family history (first-degree relative) of multiple endocrine neoplasia type 2A or type 2B, thyroid C-cell hyperplasia, or medullary thyroid carcinoma.
- [17] Evidence of hypothyroidism or hyperthyroidism based on clinical evaluation and/or an abnormal thyroid-stimulating hormone that, in the opinion of the investigator, would pose a risk to patient safety. Subjects on a stable dose of thyroid replacement therapy for at least the prior 3 months who are clinically euthyroid and who are anticipated to remain on this dose throughout the trial period may be eligible if they meet the other criteria.

- [18] Have a screening calcitonin ≥ 20 pg/mL as determined by the central laboratory at Visit 1.

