- [19] Have had any of the following within the last 6 months prior to screening: myocardial infarction (MI), unstable angina, coronary artery bypass graft, percutaneous coronary intervention (diagnostic angiograms are permitted), transient ischemic attack (TIA), cerebrovascular accident or decompensated congestive heart failure, or currently have New York Health Association Class III or IV heart failure.
- [20] Have an electrocardiogram (ECG) with abnormalities that may interfere with the interpretation of changes in ECG intervals at screening in the opinion of the investigator. A QTc (Fridericia) interval >450 ms in men and >470 ms in women is specifically excluded.
- [21] Known significant autonomic neuropathy as evidenced by urinary retention, resting tachycardia, orthostatic hypotension, or diabetic diarrhea.
- [22] Have a personal or family history of long QT syndrome, family history of sudden death in a first-degree relative (parents, sibling, or children) before the age of 40 years, or a personal history of unexplained syncope within the last year. Use of prescription or over-the-counter (OTC) medications known to significantly prolong the QT or QTc interval at screening is prohibited.
- [23] Have poorly controlled hypertension (ie, mean seated systolic blood pressure [BP] ≥ 160 mm Hg or mean seated diastolic BP ≥ 95 mm Hg) at screening, or a change in antihypertensive medications within 30 days of screening, renal artery stenosis, or evidence of labile BP including symptomatic postural hypotension.
- [24] Random fasting triglycerides >500 mg/dL (5.7 mmol/L). If the patient is on lipid-lowering therapies, doses must be stable for 30 days prior to screening.
- [25] Have an estimated glomerular filtration rate (eGFR) <45 mL/min/1.73 m², as determined by the central laboratory at Visit 1, or a level of eGFR that would contraindicate the use of metformin per the label in the respective country. Patients on metformin must meet local label requirements.
- [26] Have a history of atopy (severe or multiple allergic manifestations) or clinically significant multiple or severe drug allergies, or intolerance to topical corticosteroids, or severe post-treatment hypersensitivity reactions (including, but not limited to, erythema multiforme major, linear immunoglobulin A dermatosis, toxic epidermal necrolysis, anaphylaxis, angioedema, or exfoliative dermatitis).

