6.10.5. Laboratory Measurements

Laboratory measurements will be summarized by treatment group using descriptive statistics at each scheduled time of assessment during the treatment and follow-up periods and including any off-treatment safety follow-up visits that occur after discontinuation of study treatment.

Descriptive statistics for laboratory analyses with continuous results will include sample size, mean, SD, median, minimum, and maximum for both actual values and change from baseline.

Laboratory analyses with categorical responses will be summarized by visit and treatment group using sample size, frequency, and percentage.

A listing of laboratory measurements for individual patients will be presented by visit. An additional listing will be presented for all laboratory measurements that are outside the normal range. All laboratory measures that meet the criteria for a listing will be reported, including unscheduled and repeat or multiple measurements.

A summary report and analysis for treatment-emergent abnormal laboratory values (outside the reference ranges as appropriate) will be provided for each continuous analyte by treatment. Shift tables of the change from baseline value to the maximum/minimum postbaseline value to Week 12 for selected analytes using clinically meaningful thresholds will be summarized. A shift table for alanine aminotransferase (ALT), aspartate aminotransferase (AST), total bilirubin, and direct bilirubin will be generated using cutoff $\leq 1 \times \text{ULN}$, $> 1 \times \text{ULN}$ and $< 3 \times \text{ULN}$, $\geq 3 \times \text{ULN}$ and $< 5 \times \text{ULN}$, $\geq 5 \times \text{ULN}$ and $< 8 \times \text{ULN}$, $\geq 8 \times \text{ULN}$.

A listing of ALT, AST, and total bilirubin values at all visits will be presented for all patients who meet any of the following criteria:

- ALT $\geq 3 \times \text{ULN}$
- AST $\geq 3 \times \text{ULN}$
- total bilirubin $\geq 2 \times \text{ULN}$
- ALT or AST $\geq 3 \times \text{ULN}$ and total bilirubin $\geq 2 \times \text{ULN}$.

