6.10.6. Electrocardiograms

For ECG parameters that collected in triplicates, the arithmetic mean from the 3 measures for the same parameter at the same visit will be calculated and use for all subsequent analyses. This will include ECG heart rate (HR) in beats per minutes (bpm), QRS complex (milliseconds [msec]), and PR interval (msec), as well as the time elapsed between the onset of ventricular depolarization and the end of ventricular repolarization (QT) and QT corrected by heart rate (HR) values using Fridericia's formula (QTcF). Fridericia's correct QT formula will be reported in (msec). Descriptive statistics for the absolute values and changes from baseline for the ECG

parameters (HR, PR interval, QRS, QT, QTcF) will be presented by treatment arm. Additional summary statistics will be provided for abnormal values (categorized as Low or High as shown in Table 6.5). An MMRM-based model similar to the analysis of the primary outcome will also be used for the change from baseline in HR, PR, and QTcF.

Table 6.5. Electrocardiogram Abnormal Categories

Measure	Low	High
PR Interval	<120 msec	≥220 msec
QRS Interval	<60 msec	≥120 msec
HR	<50 and decrease of ≥15 bpm	>100 and increase ≥15 bpm
QT	NA	>500 msec
QTcF	NA	>450, >480, and >500 msec

Abbreviations: bpm = beats per minute; HR = heart rate; msec = milliseconds; NA = not applicable; QTcF = QT corrected values using Fridericia's formula.

In addition, LY3298176 concentration-response analysis of QTcF and RR results may be performed, using figures that display change from baseline in QTcF on the vertical axis versus LY3298176 concentration (from pharmacokinetics/pharmacodynamics [PK/PD]) on the horizontal axis, time-matched with the QTcF measurements. The figures will also include a regression line and corresponding regression analysis.

Summaries of categories for absolute observations and change from baseline for QTcF intervals will be provided as well, with absolute categories as >450, >480, and >500 msec and change from baseline categories as >30 msec and >60 msec.

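### SAP Table 6.5 counts ECG intervals as abnormal without regard to baseline, so an unchanged pre-dose value, such as a QTcF of 451–470 ms that the protocol allows in women at entry, is counted as High after baseline.

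*Protocol*

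**What the plan says.** **Entry.** Protocol 6.2 applies its criteria at one visit: "Patients will be excluded from study enrollment if they meet any of the following criteria at screening". Criterion [20] adds: "A QTc (Fridericia) interval >450 ms in men and >470 ms in women is specifically excluded". Its first sentence also lets the investigator exclude ECG abnormalities that would make interval changes hard to read. It gives no numeric limit for PR or QRS.

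**Which ECG.** Protocol Section 2, footnote e: "Local ECGs will be collected for screening (Visit 1) and Early Termination". The other designated visits, including Visit 3, use centralized triplicate recordings. SAP 6.1 takes Visit 3 as baseline.

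**Analysis.** SAP 6.10.6: "Additional summary statistics will be provided for abnormal values (categorized as Low or High as shown in Table 6.5". In that table:

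- QTcF is High at ">450, >480, and >500 msec", with no split by sex;
- QT is High above 500 ms;
- PR is Low below 120 ms and High from 220 ms;
- QRS is Low below 60 ms and High from 120 ms;
- heart rate is High only at ">100 and increase ≥15 bpm", and its Low category likewise requires a fall of at least 15 bpm.

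The section closes with a further QTcF summary, "with absolute categories as >450, >480, and >500 msec and change from baseline categories as >30 msec and >60 msec". It also plans descriptive changes from baseline for heart rate, PR, QRS, QT and QTcF, and an MMRM on change for heart rate, PR and QTcF.

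**The concern.** The protocol accepts a QTcF of 451–470 ms in a woman as compatible with entry, and the SAP then counts the same value in a table of abnormal ECG categories. Because eligibility rests on a local screening ECG and baseline is a later central triplicate, a patient of either sex may also be above a cut-off at Visit 3 before the first dose.

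Elsewhere the SAP usually ties an abnormal category to baseline. Every vital-sign category in Table 6.4 needs a change. Section 6.10.5 plans "A summary report and analysis for treatment-emergent abnormal laboratory values". Section 6.10.4.5 splits pancreatic enzymes by normal or raised baseline, and 6.10.4.6 requires a calcitonin rise of at least 50% as well as an absolute level. The PR, QRS, QT and QTcF rows have no such condition, and no shift table is planned for them.

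What is at stake is how a small count is read. With about 23 patients per arm, a reader who sees one or two patients above 450 ms in one titration scheme and none on placebo cannot tell from that table whether the values arose on treatment or were there before it.

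**Working it through.** The plan states no figure on this point, so there is none to reproduce. The check applies the SAP's cut-offs to example patients and then sizes the count.

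**1. Classification.** Inputs: Table 6.5 QTcF cut-offs (450, 480, 500 ms) and change categories (>30, >60 ms), SAP 6.10.6.

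| Patient | Baseline → later (ms) | Absolute category | Change category |
|---|---|---|---|
| Woman, stable | 451 → 451 | >450 | none |
| Woman, stable | 460 → 460 | >450 | none |
| Woman, stable | 470 → 470 | >450 | none |
| Either sex, stable | 450 → 450 | none | none |
| Woman, rising | 420 → 451 | >450 | >30 |
| Woman, rising | 455 → 486 | >450, >480 | >30 |

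The stable woman at 451 ms and the woman who rose from 420 to 451 ms fall in the same absolute category. Only the separate change summary distinguishes them. By contrast, an unchanged heart rate of 105 bpm is not counted, because its row needs a rise of at least 15 bpm.

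**2. Overlap with the entry limits.** The highest QTcF allowed at screening is 470 ms. Since 450 < 470 < 480, the overlap reaches the >450 ms category only.

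**3. Weight of one patient.** 1/23 = 4.3 percentage points.

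**4. How many patients (illustration).** The documents give neither the proportion of women, f, nor the share of them at 451–470 ms, q. Both are assumptions. Expected number = n × f × q.

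- Low end, f = 0.30, q = 0.01: 23 × 0.003 = 0.07 per arm; 92 × 0.003 = 0.3 in the trial.
- Middle, f = 0.50, q = 0.05: 23 × 0.025 = 0.6 per arm; 92 × 0.025 = 2.3 in the trial.
- High end, f = 0.60, q = 0.10: 23 × 0.06 = 1.4 per arm; 92 × 0.06 = 5.5 in the trial.

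**5. Chance imbalance with no drug effect (illustration).** Let x = (1 − f·q)^23 be the probability that an arm has no such patient. For one given scheme, P(scheme ≥1, placebo 0) = x(1 − x). For at least one of three schemes it is x(1 − x³). With f = 0.50:

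| q | x | One given scheme | Any of three |
|---|---|---|---|
| 0.02 | 0.794 | 0.16 | 0.40 |
| 0.04 | 0.628 | 0.23 | 0.47 |
| 0.08 | 0.391 | 0.24 | 0.37 |
| 0.095 | 0.327 | 0.22 | 0.32 |

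The product x(1 − x) cannot exceed 0.25, so for one scheme against placebo the chance is at most one in four at any assumed prevalence. The reverse pattern, placebo ≥1 and the scheme 0, is equally likely.

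**The case against.** The strongest reply is that the table does what it says. SAP 6.10.6 describes absolute categories and change categories as two complementary displays, and a stable 460 ms belongs in the first. A reader might infer that the SAP reports such values as on-treatment or treatment-emergent abnormalities. It does not use either label for these counts.

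A reader might also infer that the QTc comparison with placebo is distorted. That is not supported. The comparison is made in the MMRM on change, which by SAP 6.1.1 has the baseline value as a covariate, and an unchanged value enters it as zero change. No test is specified on the counts, and the randomised placebo arm is subject to the same cut-offs. PR is also in the MMRM, and QRS has change summaries. The any-of-three column above should not be read as the chance of a false QTc signal: it rests on assumed inputs, pools three arms and concerns one descriptive count.

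Three further points have some force. SAP 6.1 summarises safety data at each scheduled visit by default, and Visit 3 has an ECG, so baseline counts by arm would probably appear. The investigator-judged part of criterion [20] gives some protection for PR and QRS. SAP 6.10.5 itself lists liver values by absolute level alone, so the SAP uses both approaches.

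What survives is narrow. Separate counts at baseline and at later visits do not link the two within a patient. PR and QRS have no change categories, and QRS is not in the MMRM.

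**Conclusion.** The point holds as a reporting gap in a descriptive safety table. The cut-offs and the missing baseline condition are plain in the text. An unchanged pre-dose value can be counted as Low or High after baseline, most clearly for women with QTcF of 451–470 ms. Each such patient is worth 4.3 percentage points of an arm. How many there will be depends on the sex split and the QTcF distribution, which the documents do not give. Under the assumed ranges it is between about 0.3 and 5.5 patients in the whole trial.

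The primary analysis, sample size and error rate are untouched. The mismatch with criterion [20] does not imply that the eligibility limit should change, nor that the SAP's lowest category should be raised to >470 ms for women. With that cut-off, a woman moving from 420 to 465 ms would no longer appear in the lowest absolute category.

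**What to change.** Add one sentence to SAP 6.10.6: keep the absolute cut-offs as they are, including >450 ms for both sexes, and present the QTcF, QT, PR and QRS categories by Visit 3 baseline status. Either of two forms would do:

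- a shift table of baseline category against maximum postbaseline category (minimum for the Low categories of PR and QRS); or
- a count of patients newly in a category, with the denominator restricted to those not in it at baseline.

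Apply the same rule to the QTcF category summary at the end of the section. This separates pre-existing values from new ones but does not screen out small crossings: a man going from 445 to 451 ms would still be newly High. The >30 and >60 ms categories should therefore stay alongside.

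The cost is the sentence, table programming and slightly smaller denominators for the newly abnormal counts. No data collection, eligibility rule or patient management changes.

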6.3. Lifestyle Restrictions

Study participants should be instructed not to donate blood or blood products during the study or for 60 days following the study.

6.4. Screen Failures

Individuals who do not meet the criteria for participation in this study (screen failures) may be rescreened only once at the discretion of the investigator. Before rescreening is performed, the patient must sign a new informed consent form (ICF) and receive a new identification number. If, in the opinion of the investigator, an ineligible lab test result is the result of an error or extenuating circumstance, then that parameter can be retested once (if feasible within the time constraints of the screening period) without the patient having to be rescreened. However, screen failures for HbA1c may not be retested or rescreened.

7. Treatments

7.1. Treatments Administered

In this study, patients will receive treatment with 1 of 3 LY3298176 titration schemes for 3 months to assess the reduction in HbA1c compared with placebo. The titration doses of LY3298176 will range from 2.5 mg through 15 mg to reach either 12 mg or 15 mg as the highest titrated maintained dose. Study drug will be supplied as lyophilized drug in a vial and each vial will contain 5 mg. There will be matching placebo vials. Patients will receive 1 to 3 injections of study drug per week depending on which dose the patient is scheduled to receive in the titration schedule. At the highest dose attained, 12 mg or 15 mg, patients will receive 3 injections per week (to be taken at the same time). Each SC dose administration of study drug should be in different quadrants of the abdomen. If the recommendation following the first interim analysis of Study GPGB is to lower the highest dose of 15 mg to 12.5 mg, then the highest dose administered for Groups 1 and 2 of this study, GPGF, will also be lowered to 12.5 mg from 15 mg. The high dose for Group 3, 12 mg, will be unchanged. If this change occurs, it will be prior to the first patient visit for Study GPGF. Furthermore, patient user materials will be modified to indicate that the highest titrated LY3298176 dose for Groups 1 and 2 will be 12.5 mg.

This study will involve dose titration in 2.5 mg, 4 mg, 5 mg, or 7.5 mg dose increments (Table GPGF.3). Although the investigators and patients will know which titration group the patients are assigned, they will not know whether they are receiving LY3298176 or a complementary volume of placebo.

Patients will be required to dilute study drug in the vials and administer injections of the study drug or matching placebo at approximately the same time each week. The study site will send vials, diluent (Sterile Water for Injection), and syringes with needles home with patients. For all clinical site visits, the patient should dilute the vials and administer the study drug at the clinical research site under the supervision of study personnel in order to reinforce patient understanding and confidence. Patients will be diluting study drug in the vials and self-injecting at home during weeks without a clinical site visit and instructions will be provided. The investigator or site staff may assist patients with vial reconstitution and study drug injection any time they deem necessary.

Table GPGF.3. Study Treatments and Dose Titration

Study Phase	Random-ization	Treatment Phase										
		4	5	N/S	6	N/S	N/S	N/S	8	N/S	N/S	N/S
Visit	3	4	5	N/S	6	N/S	N/S	N/S	8	N/S	N/S	N/S
Week	0	1	2	3	4	5	6	7	8	9	10	11
Dose number	1	2	3	4	5	6	7	8	9	10	11	12
Titration schemes (dose in mg)												
Group 1	2.5	2.5	5	5	10	10	10	10	15	15	15	15
Group 2	2.5	2.5	2.5	2.5	7.5	7.5	7.5	7.5	15	15	15	15
Group 3	4	4	4	4	8	8	8	8	12	12	12	12

Abbreviation: N/S= none scheduled.

Note: For each of the groups, visits are scheduled to occur on the day of the next scheduled titrated dose. For non-scheduled visits, it is expected that the patient will dilute study drug and self-inject at home. However, the investigator may have the patient come to the site for an unscheduled visit to dilute the vials and self-inject at any time the investigator feels that the patient would benefit from added instruction and supervision. Visit 10 (not shown) will occur 1 week after the last dose of study drug (Dose 12).

Patients taking background metformin (either immediate release or extended release) are strongly encouraged to remain on the same type of metformin during the trial, if possible. Changing formulations or manufacturers of metformin during the study participation should be minimized. If a dose change (ie, conversion of extended release to immediate release or vice versa) is required, the investigator should determine the most appropriate clinically equivalent metformin dose. The metformin dose should be at least 1000 mg/day and not more than the highest dose allowed per local label.

The patient receiving metformin should continue the baseline dose of metformin, unless the patient experiences documented hypoglycemia, in which case the dose may be reduced.

The investigator or his/her designee is responsible for the following:

- explaining the correct use of the investigational agents to the patient or the patient's legal representative
- verifying that instructions are followed properly
- maintaining accurate records of investigational product dispensing and collection
- at the end of the study returning all unused medication to Lilly, or its designee, unless the sponsor and sites have agreed that all unused medication is to be destroyed by the site, as allowed by local law.

Patients will be instructed to contact the investigator as soon as possible if he/she has a complaint or problem with the study drug so that the situation can be assessed.

